7.5. Preparation/Handling/Storage/Accountability

Only participants enrolled in the study may receive IP and only authorized site staff may supply or administer study treatment. All study treatments should be stored in an environmentally controlled and monitored (manual or automated) area in accordance with the labeled storage conditions with access limited to the investigator and authorized site staff.

The investigator, institution, or the head of the medical institution (where applicable) is responsible for study treatment accountability, reconciliation, and record maintenance (such as receipt, reconciliation, and final disposition records).

7.6. Treatment Compliance

The IP will be administered at the CRU, and documentation of treatment administration will occur at the CRU.

7.7. Concomitant Therapy

If the need for concomitant medication arises, inclusion or continuation of the subject may be at the discretion of the investigator after consultation with a Lilly clinical pharmacologist or clinical research physician. Any additional medication used during the course of the study must be documented.

7.8. Treatment after the End of the Study

This section is not applicable for this study.

8. Discontinuation Criteria

8.1. Discontinuation from Study Treatment

Discontinuation of the IP for abnormal liver tests **should be considered** by the investigator when a subject meets one of the following conditions after consultation with the Lilly-designated medical monitor:

- Alanine aminotransferase (ALT) or aspartate aminotransferase (AST) >5X upper limit of normal (ULN)
- ALT or AST >3X ULN along with one of the following criteria
 - sustained for more than 2 weeks or
 - total bilirubin level (TBL) >2X ULN or
 - prothrombin time >1.5X ULN or
 - the appearance of fatigue, nausea, vomiting, right upper-quadrant pain or tenderness, fever, rash, and/or eosinophilia (>5%)
- Alkaline phosphatase (ALP) >3X ULN
- ALP>2.5X ULN and TBL >2X ULN
- ALP>2.5 ULN with the appearance of fatigue, nausea, vomiting, right quadrant pain or tenderness, fever, rash, and/or eosinophilia (>5%)

In addition, subjects will be discontinued from the IP in the following circumstances:

- The investigator decides that the subject should be discontinued from the IP
- The subject requests to be discontinued from the IP
- Subject experiences an SAE or clinically significant event that is related to LY3337641 administration, or
- Subject experiences moderate treatment-related AEs that impair normal activities

When this situation arises, the investigator should inform a Lilly clinical pharmacologist or clinical research physician.

When subjects discontinue the IP early, procedures to be performed will be discussed between the investigator and the Lilly clinical pharmacologist or clinical research physician.

8.1.1. Discontinuation of Inadvertently Enrolled Subjects

If the Sponsor or investigator identifies a subject who did not meet enrollment criteria and was inadvertently enrolled, a discussion must occur between the Lilly clinical pharmacologist or clinical research physician and the investigator to determine if the subject may continue in the study. If both agree it is medically appropriate to continue, the investigator must obtain documented approval from the Lilly clinical pharmacologist or clinical research physician to allow the inadvertently enrolled subject to continue in the study with or without continued treatment with IP.

8.2. Discontinuation from the Study

Subjects will be discontinued in the following circumstances:

- Enrollment in any other clinical trial involving an IP or enrollment in any other type of medical research judged not to be scientifically or medically compatible with this study
- Participation in the study needs to be stopped for medical, safety, regulatory, or other reasons consistent with applicable laws, regulations, and good clinical practice
- Investigator Decision
 - the investigator decides that the subject should be discontinued from the study
 - if the subject, for any reason, requires treatment with another therapeutic agent that has been demonstrated to be effective for treatment of the study indication, discontinuation from the study occurs prior to introduction of the new agent
- Subject Decision
 - the subject or designee (for example, parents or legal guardian) requests to be withdrawn from the study

Subjects who discontinue the study early will have end-of-study procedures performed as shown in the Schedule of Activities (Section 2).

8.3. Subjects Lost to Follow-up

A subject will be considered lost to follow-up if he or she repeatedly fails to return for scheduled visits and is unable to be contacted by the study site. Site personnel are expected to make diligent attempts to contact subjects who fail to return for a scheduled visit or were otherwise unable to be followed up by the site.

9. Study Assessments and Procedures

Section 2 lists the Schedule of Activities, detailing the study procedures and their timing (including tolerance limits for timing).

Appendix 2 lists the laboratory tests that will be performed for this study.

Appendix 5 provides a summary of the maximum number and volume of invasive samples, for all sampling, during the study.

Unless otherwise stated in subsections below, all samples collected for specified laboratory tests will be destroyed within 60 days of receipt of confirmed test results. Certain samples may be retained for a longer period, if necessary, to comply with applicable laws, regulations, or laboratory certification standards.

Investigators must document their review of each laboratory safety report.

9.1. Efficacy Assessments

This section is not applicable for this study.

9.2. Adverse Events

Investigators are responsible for monitoring the safety of subjects who have entered this study and for alerting Lilly or its designee to any event that seems unusual, even if this event may be considered an unanticipated benefit to the subject.

The investigator is responsible for the appropriate medical care of subjects during the study.

The investigator remains responsible for following, through an appropriate health care option, AEs that are serious or otherwise medically important, considered related to the IP or the study, or that caused the subject to discontinue the IP before completing the study. The subject should be followed until the event resolves, stabilizes with appropriate diagnostic evaluation, or is reasonably explained. The frequency of follow-up evaluations of the AE is left to the discretion of the investigator.

After the ICF is signed, study site personnel will record, via eCRF, the occurrence and nature of each subject's preexisting conditions, including clinically significant signs and symptoms of the disease under treatment in the study. Additionally, site personnel will record any change in the condition(s) and the occurrence and nature of any AEs.

The investigator will interpret and document whether or not an AE has a reasonable possibility of being related to study treatment, or a study procedure, taking into account the disease, concomitant treatment, or pathologies.

A "reasonable possibility" means that there is a cause-and-effect relationship between the IP, study device, and/or study procedure and the AE.

Planned surgeries should not be reported as AEs, unless the underlying medical condition has worsened during the course of the study.

If a subject's IP is discontinued as a result of an AE, study site personnel must report this to Lilly or its designee via eCRF.

9.2.1. Serious Adverse Events

An SAE is any AE from this study that results in one of the following:

- death
- initial or prolonged inpatient hospitalization
- a life-threatening experience (that is, immediate risk of dying)
- persistent or significant disability/incapacity
- congenital anomaly/birth defect
- events considered significant by the investigator based upon appropriate medical judgment

Study site personnel must alert Lilly, or its designee, of any SAE within 24 hours of investigator awareness of the event via a sponsor-approved method. If alerts are issued via telephone, they are to be immediately followed with official notification on study-specific SAE forms. This 24-hour notification requirement refers to the initial SAE information and all follow-up SAE information.

Pregnancy (maternal or paternal exposure to IP) does not meet the definition of an AE. However, to fulfill regulatory requirements any pregnancy should be reported following the SAE process to collect data on the outcome for both mother and fetus.

9.2.1.1. Suspected Unexpected Serious Adverse Reactions

Suspected unexpected serious adverse reactions (SUSARs) are serious events that are not listed in the Investigator's Brochure and that the investigator identifies as related to the IP or procedure. United States 21 CFR 312.32 and European Union Clinical Trial Directive 2001/20/EC and the associated detailed guidances or national regulatory requirements in participating countries require the reporting of SUSARs. Lilly has procedures that will be followed for the recording and expedited reporting of SUSARs that are consistent with global regulations and the associated detailed guidances.

9.2.2. Complaint Handling

Lilly collects product complaints on IPs and drug delivery systems used in clinical trials in order to ensure the safety of study participants, monitor quality, and to facilitate process and product improvements.

Subjects should be instructed to contact the investigator as soon as possible if he or she has a complaint or problem with the IP or drug delivery system so that the situation can be assessed.

9.3. Treatment of Overdose

For the purposes of this study, an overdose of LY3337641 is considered any dose higher than the dose assigned through randomization.

Refer to the Investigator's Brochure.

9.4. Safety

9.4.1. Laboratory Tests

For each subject, laboratory tests detailed in [Appendix 2](#) should be conducted according to the Schedule of Activities (Section [2](#)) and as clinically indicated.

9.4.2. Vital Signs

For each subject, vital sign measurements including body (oral) temperature, supine and standing blood pressure, and pulse rate should be conducted according to the Schedule of Activities (Section [2](#)) and as clinically indicated.

Subjects will rest in the supine position for at least 5 minutes and have supine blood pressure and pulse rate measured. Subjects will then stand for 3 minutes and have standing blood pressure and pulse rate measured.

If the subject feels unable to stand, only supine vital signs will be recorded.

Unscheduled orthostatic vital signs should be assessed, if possible, during any AE of dizziness or posture-induced symptoms. Additional vital signs may be measured during each study period if warranted and agreed upon between the sponsor and investigator.

9.4.3. Electrocardiograms

For each subject, ECGs should be collected according to the Schedule of Activities (Section [2](#)) as clinically indicated and the study-specific recommendations included in the Manual of Operations for the study.

Any clinically significant findings from ECGs that result in a diagnosis and that occur after the subject receives the first dose of the IP should be reported to Lilly, or its designee, as an AE via eCRF.

For each subject, a 12-lead digital ECG will be collected in triplicate according to the Schedule of Activities (Section [2](#)). ECGs must be recorded before collecting any blood for safety or PK tests. Subjects must be supine for approximately 5 to 10 minutes before ECG collection and remain supine but awake during ECG collection. Consecutive triplicate ECGs will be obtained at approximately 1-minute intervals. ECGs may be administered at additional times, when deemed clinically necessary.

ECGs will be interpreted by a qualified physician (the investigator or qualified designee) at the site as soon after the time of ECG collection as possible, and ideally while the subject is still

present, to determine whether the subject meets entry criteria at the relevant visit(s) and for immediate subject management, should any clinically relevant findings be identified.

If a clinically significant quantitative or qualitative change from baseline is identified after enrollment, the investigator will assess the subject for symptoms (for example, palpitations, near syncope, syncope) to determine whether the subject can continue in the study. The investigator or qualified designee is responsible for determining if any change in subject management is needed and must document his or her review of the ECG printed at the time of evaluation from at least 1 of the triplicate ECGs from each time point.

Digital ECGs will be electronically transmitted to a central ECG laboratory designated by Lilly. The central ECG laboratory will perform a basic quality control check (for example, demographics and study details) then store the ECGs in a database. At a future time, the stored ECG data may be overread at the central ECG laboratory for further evaluation of machine-read measurements or to meet regulatory requirements.

The machine-read ECG intervals and heart rate may be used for data analysis and report writing purposes unless a cardiologist overread of the ECGs is conducted prior to completion of the final study report (in which case the overread data would be used).

9.4.4. Other Tests

9.4.4.1. Assessment and Management of Subjects Developing a Rash

Subjects who develop a rash should be evaluated as soon as possible. Investigators will be prompted to categorize and diagnose the rash (per clinical judgment), assess relatedness to IP, and grade its severity. This information will be recorded on the source document and entered into the eCRF. Additional information related to the rash evaluation will also be recorded on the source document and will include a history of infections and allergies and recent exposure to prescription or over-the-counter medications, skin products, detergents, or other potential skin irritants. A review of systems will be completed to assess for systemic symptoms and concurrent illnesses. A symptom-directed physical examination should be performed, including an evaluation of the rash distribution and type, vital signs and temperature, and other organ systems, as clinically indicated. In addition, photographs and laboratory measurements should be obtained as clinically indicated, according to investigator judgment. The subject should be evaluated to determine whether there are any signs or symptoms suggesting a severe, potentially life-threatening condition.

If a subject develops a rash that is assessed as not related to IP, is transient, or is not clinically significant in the opinion of the investigator, the IP may be continued without interruption. In some cases, the investigator may instead choose to interrupt the IP and restart it at a later date. The dates for stopping and restarting the IP should be captured. Immediate and permanent discontinuation of IP should be considered for all subjects with clinically significant rash. For rashes deemed clinically significant, punch biopsy of the rash may also be performed. In addition, a venous blood sample may be collected for PK analysis at the time of evaluation with documentation of the date and time of administration of the most recent dose of IP.

Subjects should be followed up until resolution of the rash, to the extent possible. The site should manage any rash that occurs during the study according to the judgment of the investigator. Interventions may include supportive care, pharmacotherapy, laboratory evaluation, additional skin biopsies, and consultation with a dermatologist, as clinically indicated. Data from these additional interventions should be provided to the sponsor as part of the AE reporting after being deidentified and summarized by the investigative site.

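### For a related rash that is clinically significant, or moderate and activity-limiting, Protocol 8.1 requires the product to be stopped while Protocol 9.4.4.1 leaves it to judgement, and nothing says which governs

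*Protocol*

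**What the plan says.** Protocol Section 8.1 has two tiers. For abnormal liver tests, stopping the product is something the investigator should consider. The section then changes verb: "In addition, subjects will be discontinued from the IP in the following circumstances". Two items on that second list matter here:

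- "Subject experiences an SAE or clinically significant event that is related to LY3337641 administration"
- "Subject experiences moderate treatment-related AEs that impair normal activities"

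The list has no exception for rash and does not mention Section 9.4.4.1.

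Protocol Section 9.4.4.1 deals with rash specifically. Its continuation rule reads, in part: "assessed as not related to IP, is transient, or is not clinically significant in the opinion of the investigator, the IP may be continued". No pause in dosing is needed in those cases. It then gives the investigator the option of pausing the product and restarting it later. For more serious cases it says: "Immediate and permanent discontinuation of IP should be considered for all subjects with clinically significant rash". It closes by leaving the management of any rash to the investigator's judgement, and it does not mention Section 8.1.

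**The concern.** The same rash can fall under both sections and receive instructions of different force. An investigator faced with a rash would naturally turn to the section written for it. Under that section, dosing can continue, or be paused and resumed, in a subject whom 8.1 says will be stopped.

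Rash is not a side issue in this protocol. It is the only adverse event named in the sponsor's periodic review (Section 9.4.5), and skin inspections are scheduled throughout both Schedules of Activities. Safety and tolerability is the primary objective. Which section is followed affects:

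- whether a subject with such a rash goes on being dosed;
- how many subjects are reported as having stopped the product;
- who receives the Day 15 dose, on which the last-dose PK, BTK occupancy and ECG profiles depend. SAP Section 6 gives 30 mg QD on Day 15 its own column for PK, vital signs and ECG.

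**Working it through.** No figure in the plan depends on this point, so the check is a comparison of the two texts, followed by a count of the subjects to whom it could apply.

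**Step 1: the verbs.** Section 8.1 uses *should be considered* for liver tests and *will be discontinued* for its second list. The change within one section indicates that the difference is intended. Section 9.4.4.1 uses the weaker verb, and applies it to every subject with a clinically significant rash, which includes those whose rash is related.

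**Step 2: the continuation rule.** Its three conditions (unrelated, transient, not clinically significant) are joined by *or*. Any one is enough, so a related rash qualifies if it is transient.

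**Step 3: the cases side by side.** The table takes non-serious rashes where neither the subject nor the investigator has independently decided to stop.

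| Rash | Section 8.1 | Section 9.4.4.1 | Agree? |
|---|---|---|---|
| Unrelated, clinically significant | Related-event items do not apply | Consider stopping; may also continue because unrelated | No conflict between sections |
| Related, clinically significant | Will be stopped | Consider stopping | **No** |
| Related, moderate, limits activities, transient | Will be stopped | May continue | **No** |
| Related, moderate, limits activities, judged not clinically significant | Will be stopped | May continue | **No** |
| Related, not clinically significant, not activity-limiting | Neither item applies | May continue | Yes |

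The collision is confined to related rashes that meet one of the two items in 8.1.

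**Step 4: is there a ranking rule?** Neither section cites the other, and no general clause says which prevails. The protocol does write such clauses elsewhere: Appendix 6 says the protocol's content overrides the blinding table.

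**Step 5: who could be affected.** Single-dose subjects have no later dose to withhold, so only the multiple-dose cohorts count. From Protocol Section 5.1:

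- Cohort 1: 8 Japanese + 4 Caucasian = 12 subjects.
- Optional Cohort 5 at its planned size: 8 + 4 = 12 subjects.
- Total: 12 + 12 = 24 subjects.

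Placebo subjects are included because the investigator is blinded (Sections 5.1 and 7.3, Appendix 6) and must judge relatedness without knowing the assignment. The Figure JPDB.1 footnote allows the size of Cohort 5 to change.

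**Step 6: frequency.** This would be the number of multiple-dose subjects multiplied by the probability of a rash on which the two sections give different decisions. The documents give no rash rate, so that probability is unknown and no estimate is offered.

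**The case against.** The best counter-argument is that both sections can be obeyed at once. Considering a stop does not forbid it, so an investigator who stops a related, clinically significant rash under 8.1 has also met 9.4.4.1. The continuation rule is only a permission, and it sits in a section on other tests rather than in the chapter on discontinuation criteria. The rash sentence also concerns a stop that is both immediate and permanent, qualifiers absent from 8.1, so it might be answering a different question.

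It is true that one course of action satisfies both sections. That does not make the sections consistent. If 8.1 always controls, the discretion in 9.4.4.1 has no effect for the three conflicting rows of the table. If 9.4.4.1 is meant as an exception, 8.1 should say so. A reader might infer that 8.1 is the floor, or that the more specific section prevails, but the protocol states neither principle.

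A reader might also infer that subjects are left unprotected. The documents do not support that. Section 9.4.4.1 requires prompt evaluation, grading, a relatedness assessment and a check for severe conditions. Section 8.1 lets the investigator stop the product for any reason and has the sponsor's physician or pharmacologist informed. Section 9.4.5 puts rash in the sponsor's periodic review.

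**Conclusion.** The point holds as an internal contradiction: wrong as written. For a related rash that is clinically significant, or moderate and activity-limiting, Section 8.1 is mandatory and Section 9.4.4.1 discretionary, with no text to settle which applies. It does not extend to unrelated rashes or to the single-dose cohorts.

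The decision could arise for any of the 12 subjects in Cohort 1, and for up to 24 with Cohort 5. That rests on Cohort 5 being run at its planned size and on the investigator remaining blinded. How often the two rules would lead to different decisions is not known.

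Two stronger readings go too far:

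- A reader might count only subjects on LY3337641: 6 + 3 = 9 per multiple-dose cohort, or 18 in two. The blinded investigator cannot make that distinction, so the decision is not limited to them.
- A reader might infer that the wording costs a third of the Caucasian Day 15 data, since 3 Caucasian subjects per multiple-dose cohort receive LY3337641 and 1/3 = 33%. That fraction would follow from any one such discontinuation and does not measure the effect of the wording. Section 10.1 also allows a subject who leaves the study to be replaced within cohort and race, at the sponsor's discretion. Section 8.1 leaves procedures after an early stop to case-by-case agreement, so losing all Day 15 safety data cannot be assumed. The on-treatment Day 15 profile of a subject who stops before that dose would be lost.

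**What to change.** Reconcile Sections 8.1 and 9.4.4.1 so that one rule covers a related rash that is clinically significant, and one that is moderate and limits normal activities. The reconciled text should deal expressly with the transient case and with interruption and restart. Add a cross-reference in each section stating which governs. The clinical team decides what the rule is; no view is taken here.

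The cost is a sentence or two in a protocol amendment. Amendment (a) already resolved a similar mismatch between two sections, on Day 15 dosing. The sample size, the Schedule of Activities and the SAP analyses need no change.
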